7.1 Overview of Study Interactions

Each Treatment subject will undergo the following formal study interactions:

- Baseline Assessment
- LUX-Dx Insertion (Enrollment to Day 7 post Index Procedure, highly recommended to occur 30 days prior to Index Procedure)
- Index Procedure / Rescheduled Index Procedure (Day 0)
- Pre-Discharge Assessment (immediately prior to discharge after the Index Procedure)
- Day 7 Safety Assessment (window Day 7 – 11, remote)
- Day 30 Safety Assessment (window Day 30-37, remote)
- Day 90 Assessment (window 90 ± 14 days, in-person)
- Day 180 Assessment (window 180 ± 30 days, remote)
- Day 360 Assessment (window 360 ± 30 days, in-person)

In addition, the following events may also occur for some study subjects:

- Re-ablation Procedure: Re-ablations for AF, AFL and AT will be captured in the EDC database using the Re-Ablation Procedure CRF
- Unscheduled Assessments: Any unscheduled cardiovascular assessments will be captured in the EDC database using the Unscheduled Assessment CRF.

The data collection schedule for these various interactions is shown in **Table 7.2-1**.

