Only 2-minute windows occurring after the blanking period will be used for analysis. Thirty-day intervals will repeat until an interval contains an in-window Day 360 Assessment, Day 390, or subjects' End of Study date, whichever occurs first. In the final 30-day interval, only 2-minute windows occurring on or prior to the in-window Day 360 Assessment, Day 390, or subjects' End of Study date, will be used for analysis. If a 2-minute window occurs on the same day as a scheduled study visit (Day 180 or Day 360 Assessment) or on the same day as the simulated Holter patch, then a new 2-minute window will be randomly selected to avoid overlapping with the 12-lead ECG recording and simulated Holter patch recording.

Twenty-four (24) hour Holter patches will be simulated by selecting LUX-Dx data from the day before the Day 180 and Day 360 Assessments. The day before was selected to avoid overlapping with the 12-Lead ECG recordings from each visit. For subjects that had a missed visit for the Day 180 or Day 360 assessment, the last day of the subject's visit window will be used for the simulated Holter patch.

Recurrence will be defined as a stored LUX-Dx AT or AF episode that is adjudicated as containing at least 30 seconds of atrial arrhythmia and that overlaps a simulated window by any amount. Additionally, all LUX-Dx recorded symptomatic episodes and all 12-lead ECGs will be assessed for AF, AFL, or AT recurrence as defined in Protocol Section 23.2.

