8.3.3.5 Sensitivity of Effectiveness to the timing of Day 360 Assessment

For the PEE, if the Day 360 Assessment is completed late (after Day 390) only events that occurred within window count as Treatment Failures, as described in Appendix A of the ADVANTAGE AF SAP. In this sensitivity analysis, the PEE will be calculated counting events that occur outside of the visit window (after Day 390) as Treatment Failures.

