Detectable AF, AFL, or AT	
Detectable AF, AFL or AT is an episode of AF, AFL or AT which:
 
 • Is recorded for review on a LUX-Dx ICM and meets any of the following criteria: 
 ○ Adjudicated symptomatic (patient initiated) recording that contains ≥ 30 seconds of continuous atrial arrhythmia. ○ Adjudicated AF or AT episode captured by LUX-Dx that contains at least 30 seconds of atrial arrhythmia and overlaps a simulated bi-monthly, 2 minute event monitor transmission period. ○ Adjudicated AF or AT episode captured by LUX-Dx that contains at least 30 seconds of atrial arrhythmia and overlaps a simulated 24 hour holter period occurring the day before the Day 180 and Day 360 Assessments (or last day of respective visit window if visit(s) is missed)⁸. • Continuous AF, AFL or AT for the entirety of a 12 lead ECG if the continuous interpretable signal is 10 seconds or longer • Exclusions: 
 ○ CTI isthmus-dependent AFL if the subject did not have a CTI ablation with the FARAPoint PFA Catheter ○ Arrhythmias recorded on other devices, including implantable monitors and consumer wearables, not specified in the ADVANTAGE AF Study procedures
Failed AAD	
Failed AADs include any and all Class I / III AAD determined at the time of enrollment to have been failed for effectiveness or intolerance. Failed AADs do not include Class I / III AADs determined at the time of enrollment solely to be contraindicated.
 
Failed AADs must be established as part of the Baseline Assessment for agent, type of failure (arrhythmia recurrence or AAD intolerance) and the maximum failed dose (the total daily dose at which such failure occurred).

Intent Subjects	
Intent Subjects are defined in Section 6.6.3 of the ADVANTAGE Phase 1 Protocol.

Non-Failed AAD	
A Non-Failed AAD is:
 
 • Any Class I / III AAD not established at the Baseline Assessment as a Failed AAD • Any Failed AAD used after Day 90 at a daily dose exceeding the maximum failed dose established at the Baseline Assessment

⁸ Day prior to the Day 180 and Day 360 visits was selected to prevent overlap in the rhythm captured by the visit-required 12-lead ECG.

Term	Definition
Persistent atrial fibrillation	PersAF is defined as continuous AF that is sustained beyond 7 days, but not greater than 12 months duration.

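### A Day 360 visit on Day 392 or later puts its simulated Holter outside the period in which events count, whereas a missed visit keeps a countable one; the Phase 2 primary success rate is biased slightly upward.

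*Combined protocol and SAP*

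**What the plan says.** All references are to the Phase 2 plan (protocol Appendix A) unless stated.

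- **Holter day, visit done.** Section 8.1.2.3: the simulated Holters "will be simulated by selecting LUX-Dx data from the day before the Day 180 and Day 360 Assessments". No in-window condition is attached.
- **Holter day, visit missed.** The same section: "the last day of the subject's visit window will be used for the simulated Holter patch". The definition of Detectable AF, AFL, or AT in Section 23.2 repeats this: "or last day of respective visit window if visit(s) is missed". Neither place mentions a late visit.
- **Window.** Section 7.1: "Day 360 Assessment (window 360 ± 30 days, in-person", so it closes on Day 390.
- **What counts after a late visit.** Section 8.3.3.5: "if the Day 360 Assessment is completed late (after Day 390) only events that occurred within window count as Treatment Failures". The section refers to Appendix A of the SAP for this rule. In the sensitivity analysis described there, "the PEE will be calculated counting events that occur outside of the visit window (after Day 390) as Treatment Failures".
- **Simulated event monitor.** Section 8.1.2.3 does limit this part: "Thirty-day intervals will repeat until an interval contains an in-window Day 360 Assessment, Day 390, or subjects' End of Study date, whichever occurs first".

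**The concern.** The two halves of the simulated monitoring treat a late Day 360 visit differently. The event-monitor windows stop at Day 390 at the latest. The Holter follows the visit past Day 390, into a period where the primary analysis ignores events. A subject who attends late therefore has less countable monitoring than one who does not attend, and no reason is given.

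Late cannot simply be read as missed. Section 8.3.3.4 lists late and missed Day 90 visits as two cases, and Section 8.3.3.5 has a rule of its own for a late Day 360 visit.

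The placement also departs from what is being simulated. Section 8.1.2 carries over the Phase 1 assumptions because the simulated periods are meant to imitate Phase 1 monitoring, and Phase 1 Section 7.12 puts the Day 360 Holter inside the 360 ± 30-day window.

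Fewer chances to detect recurrence can only raise observed success, in a single-arm test against a fixed goal of 40%. Section 8.3.6 also compares Phase 1 and Phase 2 success rates, so the asymmetry could carry into that comparison.

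**Working it through.** **1. The plan's own figure.** Section 8.1.2.2 gives an expected rate of 55%, a goal of 40%, one-sided alpha 0.025, 90% power, and 122 evaluable or 136 enrolled subjects. An exact binomial test with n = 122 needs at least 60 successes; alpha is 0.0248 and power 0.916. For attrition, 122 / 0.90 = 135.6, rounded up to 136. The figures reproduce. The point itself does not depend on them.

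**2. Day arithmetic.** The window ends on Day 360 + 30 = 390. With the visit on day V, the Holter day is H = V − 1, and it counts only if H ≤ 390, that is V ≤ 391.

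| Day 360 visit | Holter day | Counts in the primary analysis? |
|---|---|---|
| Day 390 | 389 | yes |
| Day 391 | 390 | yes |
| Day 392 | 391 | no |
| Day 400 | 399 | no |
| Missed | 390 | yes |

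The loss starts at Day 392. A late Day 180 visit does not lose its Holter this way.

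**3. Share of simulated monitoring time.** Two Holters are 2 × 1,440 = 2,880 minutes. Two two-minute windows per 30 days over about 270 days give 18 × 2 = 36 minutes. One Holter is 1,440 / (2,880 + 36) = 49.4% of the total (49.3% with 20 windows).

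**4. Chance of detection (episode patterns are assumptions).** Let asymptomatic episodes occur at random at rate r per day, each lasting d days. With k Holters and 18 windows:

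P(detected) = 1 − exp{−[k·r(d + 1) + 18·r(d + 2/1440)]}

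| Episodes over 270 days | Burden | Two Holters | One Holter | Difference |
|---|---|---|---|---|
| 60 of 1 hour | 0.9% | 47.0% | 33.2% | 13.8 points |
| 27 of 3 hours | 1.25% | 36.4% | 28.8% | 7.6 points |
| 12 of 6 hours | 1.1% | 26.8% | 22.6% | 4.2 points |

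All three are low-burden. With 24-hour episodes and 20 windows, two versus one Holter gives 91% versus 89% at 10% burden, and 99.2% versus 98.8% at 20%. The loss is therefore concentrated in low-burden recurrence.

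**5. Effect on the success rate (share of late visits assumed).**

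- Ceiling: 10% late × 13.8 points = 1.4 points, if every late attender has such a recurrence and no other failure.
- If 45% of them do (illustrative, 1 − 0.55): 1.4 × 0.45 = 0.6 points.
- Low end: 5% × 4.2 points × 0.45 = 0.09 points.

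**6. Effect on the test.** Let f be the share of subjects with a visit on Day 392 or later, and q the share of those whose only failure would be on the restored Holter. Observed success is overstated by f × q. The table gives the exact binomial probability of passing at a true rate of 40%, as a stand-in for the planned Kaplan-Meier limit. The size 232 is 258 less 10%.

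| f, q | Overstatement | n = 122 | n = 232 |
|---|---|---|---|
| none | 0 | 0.0248 | 0.0182 |
| 2%, 2% | 0.04 points | 0.0253 | 0.0188 |
| 5%, 5% | 0.25 points | 0.0283 | 0.0220 |
| 10%, 10% | 1.0 point | 0.0412 | 0.0376 |
| 20%, 10% | 2.0 points | 0.0655 | 0.0711 |

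The last row is an extreme, not an expectation.

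**The case against.** Four arguments limit the point.

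- **An unseen document may settle it.** Section 8.3.3.5 refers to Appendix A of the SAP, which was not supplied and may say where the Holter goes for a late visit. This stands as a limit on certainty. The protocol's own rule and definition would still need to agree with it.
- **Late attenders remain under observation.** A reader might infer that they are scored event-free, or that losing 49% of simulated minutes halves their chance of failing. The documents do not support this. They still fail on the event-monitor windows to Day 390, the Day 180 Holter, symptomatic recordings, in-window ECGs, re-ablation, cardioversion or disqualifying antiarrhythmic drug use. Their event-monitor windows can also run up to 60 days longer (390 − 330) than those of a subject seen early in the window. Only an asymptomatic recurrence missed by all of these is lost.
- **A sensitivity analysis exists.** A reader might infer that nothing in the plan shows the effect of the lost Holter. In fact the Section 8.3.3.5 analysis counts events after Day 390, so the late Holter does contribute there. What remains is that it also adds every other event after Day 390, never places a Holter inside the window, and leaves the primary result unchanged.
- **The effect is small.** The documents give no rate of late visits or burden distribution, and the design gap is 15 points (55% against 40%). This stands.

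**Conclusion.** The point holds on the supplied text. The Holter rule and the counting rule, read together, give a subject seen on Day 392 or later one countable Holter and a subject who misses the visit two. The direction is always favourable to the device.

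The bias in the primary success rate is probably a few tenths of a point, with about 1.4 points as the ceiling at 10% late visits. Those figures rest on assumed late-visit shares and episode patterns; a larger late share would scale them up. The inference that this alone would decide the trial is not supported when observed success is near the expected 55%. It could matter only if the lower confidence limit falls close to 40%. This is a clear inconsistency that should be corrected before the analysis, with a modest expected effect.

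**What to change.** In Section 8.1.2.3 and in the Detectable AF, AFL, or AT definition in Section 23.2, state that if the Day 360 Assessment is missed or completed after Day 390, the simulated Holter uses the last day of the visit window (Day 390). Check that Appendix A of the SAP says the same. Under this wording a Day 391 visit still uses Day 390, so nothing changes for it.

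Leave Section 8.3.3.5 unchanged as the analysis that adds events after Day 390. Do not extend the fallback to subjects who exit early: Section 8.1.2.3 already censors withdrawals and deaths, and a Holter rule for them would be a new provision.

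The cost is one sentence in each place. The monitor data are already collected and no study procedure changes. The reported success rate may fall slightly. The change should be made before the analysis, because choosing Holter days after results are known would be open to challenge.

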2.3 Non-Investigational Devices

2.3.1 LUX-Dx Insertable Cardiac Monitor

The LUX-Dx ICM is a small, leadless electronic device implanted under the skin in the left anterior chest wall. Its primary functions are to monitor, record, and store data related to cardiac arrhythmias. Two electrodes on the body of the device are used to monitor and record the patient's subcutaneous ECG (S-ECG) data when specific arrhythmias (according to the device-programmed settings) are detected, which include pause, bradycardia, tachycardia, AF, and atrial tachyarrhythmias (AT). In addition, the device will record S-ECG data when the patient triggers the device to record via the myLUX patient app. The ICM's memory can store up to 60 minutes of S-ECG recordings. Initial default arrhythmia detection parameters are provided by LATITUDE Clarity according to the Reason for Monitoring.

Figure 2-5: LUX-Dx ICM Device and Mobile App

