Tachy Response	Less	Yellow Alert
AT Detection	On	Alert for Tachy Events –
AT Duration	4 hours at 110 bpm	On Red Alert

Any programming outside of these nominal parameters prior to a confirmed recurrence of Detectable AF, AT or AFL must be entered into the EDC and justification provided.

7.7 *Index Procedure / Rescheduled Index Procedure*

7.7.1 *Index Procedure / Rescheduled Index Procedure Data Collection*

Type of Assessment: In-person at investigational site
The performance of the Index Procedure / Rescheduled Index Procedure and the Pre-Discharge Assessment both require an in-person assessment. The Index Procedure / Rescheduled Index Procedure must be deferred if this is not possible.

Procedural data will be collected including but not limited to:

- The results of transesophageal echocardiography (TEE) or volumetric CT within 48 hours prior to procedure, or intracardiac echocardiography (ICE) prior to transseptal puncture, utilized for exclusion of LA thrombus.
- Pregnancy test (all women of childbearing potential if the baseline pregnancy test was obtained more than 30 days prior to the Index Procedure / Rescheduled Index Procedure)
- Documentation of PVI for each attempted vein, of PWI, and if performed, of CTI BDB
- Post-ablation electroanatomical maps, if performed with Rhythmia
- The functional status of both phrenic nerves will be assessed radiographically pre and post ablation.
- Method of sedation or anesthesia
- Whether adenosine was used to confirm PVI and / or PWI
- Whether a post-procedure cardioversion was performed
- Adverse events
- For the 3D mapping system: Manufacturer and model, when applicable
- 12-lead ECGs pre- and post-ablation
- Procedural times
- Ablation data

- Procedural anticoagulation data:
 - For subjects on a DOAC whether DOAC therapy was interrupted for procedure
 - For subjects on warfarin, a pre-ablation international normalized ratio (INR) value
 - Procedural heparin administration and timing
- Device deficiencies and malfunctions

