8.3.3.6 Sensitivity of Effectiveness to AT/AFL Detection Method (Tipping Point Analysis)

A tipping point analysis will be performed for the PEE to assess the impact of using the LUX-Dx AT algorithm with a minimum duration setting of 4 hours to detect AT and AFL events. All Treatment subjects with PEE Success will be one by one considered to have had an undetected AT/AFL event counting as a PEE failure. The number of subjects that would need to have had an undetected AT/AFL event to fail the PEE will be considered the tipping point. The probability of the tipping point occurring will be calculated based on the rate of PEE Failures observed in ADVANTAGE AF Phase 1 that were due to AT or AFL recurrence recorded by Holter or Event Monitor with no other mode of failure. Additional details for this analysis will be included in the Statistical Analysis Plan.

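### The Phase 2 simulated event-monitor and Holter windows count only LUX-Dx episodes labelled AT or AF, so an asymptomatic atrial tachycardia or flutter stored only as a Tachy episode goes uncounted

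*Combined protocol and SAP*

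**What the plan says.** All sections are in Appendix A (Phase 2) unless marked otherwise.

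- **Simulated windows, 8.1.2.3.** "Recurrence will be defined as a stored LUX-Dx AT or AF episode that is adjudicated as containing at least 30 seconds of atrial arrhythmia", provided that it "overlaps a simulated window by any amount". The windows are two random 2-minute periods every 30 days and the 24 hours before the Day 180 and Day 360 visits.
- **Endpoint definition, 23.2.** Both simulated-window criteria under Detectable AF, AFL, or AT carry the same restriction: "Adjudicated AF or AT episode captured by LUX-Dx that contains at least 30 seconds of atrial arrhythmia".
- **Other rhythm routes.** 8.1.2.3 adds that "all LUX-Dx recorded symptomatic episodes and all 12-lead ECGs will be assessed for AF, AFL, or AT recurrence". In 23.2 the symptomatic route reads "Adjudicated symptomatic (patient initiated) recording that contains ≥ 30 seconds of continuous atrial arrhythmia", with no condition on device episode type.
- **What the device records, 2.3.1.** It stores a subcutaneous ECG for programmed arrhythmias, "which include pause, bradycardia, tachycardia, AF, and atrial tachyarrhythmias (AT").
- **Programming, Table 7.6-1.** AF detection is on with a 4-minute duration. AT detection is on with a duration of 4 hours at 110 bpm. There is a Tachy response setting and an entry "Alert for Tachy Events". No Tachy rate or duration threshold is given.
- **Known AT/AFL limitation, 8.3.3.6.** A tipping-point analysis addresses the effect of "using the LUX-Dx AT algorithm with a minimum duration setting of 4 hours to detect AT and AFL events".
- **Phase 1 rule, main protocol 23.2.** Any AF, AFL or AT on a study ECG, event monitor or Holter counts if there are at least 30 seconds of interpretable signal (10 seconds for a 12-lead ECG). CTI-dependent flutter is excluded. No device label is involved.

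**The concern.** The 55% expected rate and the 40% goal are carried over from Phase 1 unchanged. The justification in 8.1.2 is that the simulated windows reproduce Phase 1 monitoring. A Holter reader classifies whatever rhythm is on the tape. The Phase 2 rule first filters by the label that the device gave the episode and then adjudicates the rhythm.

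The filter bears on the rhythms for which detection is already weakest. Atrial tachycardia and flutter depend on an AT algorithm with a 4-hour minimum. If a shorter episode conducts fast enough to be stored as Tachy and does not meet AF detection, that strip may be its only automatic recording. The rule then leaves out a recurrence that is on file.

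Every such omission moves the scored success rate upward, in an endpoint that must beat a fixed goal. The Phase 1 versus Phase 2 comparison of detection methods in 8.3.6 inherits the same asymmetry.

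**Working it through.** **1. Following one episode through the rules.** Take an asymptomatic one-hour atrial tachycardia on the simulated Holter day, stored by the device as Tachy only.

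| Route | Does it count? |
|---|---|
| Phase 1 Holter | Yes: at least 30 seconds on a study Holter |
| Phase 2 simulated window | No: the label is neither AT nor AF |
| Phase 2 AT algorithm | Not triggered: 1 hour is below 4 hours |
| Phase 2 symptomatic recording | No: not patient-initiated |
| Phase 2 12-lead ECG | Only if the arrhythmia is present throughout a 12-lead tracing |
| Re-ablation, cardioversion, AAD use (3.4.2) | Only if one of these occurs after blanking |

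The episode itself is uncounted. The subject is a success only if the last two rows, and every other episode in that subject, are also negative.

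**2. The plan's own figure.** Inputs from Table 8.1-3: 55% expected, 40% goal, one-sided 0.025, exact binomial, 122 evaluable, 10% attrition. The smallest r with P(X ≥ r | 122, 0.40) ≤ 0.025 is 60, with probability 0.0248. Power is P(X ≥ 60 | 122, 0.55) = 0.916, against 90% stated. Attrition: 122 / 0.90 = 135.6, so 136 as stated. The sample size reproduces and does not depend on this point.

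**3. Pass boundary under the planned log-log limit.** Without censoring, L = p^exp(1.96·s), where s = √[(1 − p)/(n·p)] / |ln p|. For 120 of 258:

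- p = 0.4651 and |ln p| = 0.7655
- s = √(0.5349/120) / 0.7655 = 0.0872
- L = 0.4651^exp(0.1709) = 0.403

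For 119 of 258 the limit is 0.399. The boundary is therefore 120 of 258 (46.5%) if all 258 are LUX-Dx monitored and none is censored. At n = 122 the same formula gives 60, the same as the exact test.

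**4. Sensitivity to an assumed share.** Let m be the share of subjects whose only failure is an uncounted Tachy episode. The documents give no value, so the range is an assumption. With a true success rate of 40%, the chance of passing is P(X ≥ boundary | n, 0.40 + m):

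| m (assumed) | n = 122, boundary 60 | n = 258, boundary 120 |
|---|---|---|
| 0 | 0.0248 | 0.0197 |
| 1% | 0.0412 | 0.0418 |
| 2% | 0.0655 | 0.0804 |
| 3% | 0.0994 | 0.1410 |

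**5. At the planned rate.** 0.55 × 258 = 141.9 successes. An assumed 1% to 3% is 2.6 to 7.7 subjects. Removing 7.7 leaves 134.2, above 120.

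**The case against.** **Other failure routes exist.** A reader might infer that the plan scores a recorded flutter as treatment success. The documents do not support that. Symptomatic recordings and 12-lead ECGs count without any label filter, a reported AFL recurrence requires a 12-lead ECG, and re-ablation, cardioversion and drug use are failures. This stands as a limit on the point. It does not close the gap: none of these routes captures an asymptomatic episode that ends between visits without an intervention, and a later 12-lead ECG counts only if the arrhythmia is still present.

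**Device behaviour is not documented.** Nothing says how a fast regular atrial rhythm under 4 hours is labelled, or whether AF detection would capture it. The alert column of Table 7.6-1 is misaligned in the text available, so the Tachy alert entry is weak evidence. This stands for frequency. The separate tachycardia type in 2.3.1 and the label restriction in 8.1.2.3 and 23.2 do not depend on the table.

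**8.3.3.6 already covers missed AT/AFL.** It converts successes to failures one by one and takes its probability from Phase 1 AT/AFL-only failures on Holter or event monitor, with no label filter. That bounds the problem hypothetically and is worth keeping. It does not use strips that are already stored.

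**Adjudication is left to the Phase 2 SAP.** 11.2 sends atrial arrhythmia episodes, a broader term, to BeatLogic and defers the formal process. A reader might infer that Tachy episodes are expressly excluded. They are not; they are unnamed. But 11.2 governs which episodes are adjudicated and does not widen what counts under 8.1.2.3 and 23.2. The storage sensitivity analysis in 8.3.3.7 also names only AT, AF and patient-triggered episodes.

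**Conclusion.** As written, the simulated windows leave out an asymptomatic atrial tachycardia or flutter that is stored only as a Tachy episode, and in this they depart from the Phase 1 monitoring that they are meant to reproduce. The direction is certain: it can only raise the scored success rate.

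The size is unknown. To matter in a subject, the episode must be atrial, asymptomatic, labelled Tachy only, stored and overlapping a window, with no other failure. CTI-dependent flutter is in any case excluded for subjects not ablated with FARAPOINT, and only about 30% are expected to receive that catheter. The 1% to 3% range is an assumption with no source in the documents. The boundary of 120 of 258 assumes complete monitoring and no censoring, although 8.1.2.3 and 8.2.1 allow for both exclusions and censoring.

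Under those assumptions, a true rate of 40% would pass with probability 0.042 to 0.141 instead of 0.020. At the planned 55% the conclusion would be unlikely to change. The point matters for a result near the boundary. It is worth correcting because the recordings exist and the correction is small.

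**What to change.** - In 8.1.2.3 and in both simulated-window criteria of 23.2, count any stored LUX-Dx AF, AT or Tachy episode that overlaps a simulated window and is adjudicated as at least 30 seconds of atrial arrhythmia. Keep the existing CTI-dependent flutter exclusion.
- Name the same episode types in 8.3.3.7 and in 11.2, so that the storage sensitivity analysis and the adjudication pathway match the definition.
- Leave 8.3.3.6 as it is. Restricting it to events with no stored recording would weaken an existing safeguard.

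**Cost.** More strips go through BeatLogic, which 23.2 says classifies LUX-Dx ECGs as atrial or non-atrial arrhythmia. The documents do not show its performance on Tachy-triggered strips, so some misclassification is possible; specified events may go to the independent experts already allowed in 11.2. The success rate may be slightly lower. No sample-size input changes.
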